3. ANALYSIS SETS

3.1. Intent-to-Treat Analysis Set

The intent-to-treat (ITT) analysis set will include all randomized patients.

In the ITT analysis set, treatment will be assigned based on the treatment to which patients were randomized, regardless of which treatment they actually received.

The ITT analysis set will serve as the primary analysis set for the efficacy analyses.

3.2. Safety Analysis Set

The safety analysis set will include all randomized patients who receive at least 1 dose of IMP.

In the safety analysis set, treatment will be assigned based on the treatment patients actually received, regardless of the treatment to which they were randomized, unless otherwise specified.

The safety analysis set will be used for all analyses of safety data.

3.3. Per-Protocol Analysis Set

The per-protocol (PP) analysis set is a subset of the ITT analysis set including only patients without protocol violations that could have an effect on the primary outcome and who have greater than or equal to 80% compliance to the IMP over the entire treatment period. The compliance rate calculation is detailed in Section 8.3.

PP analysis set will be determined before unblinding at the Statistical Data Review (SDR) meeting and documented in the SDR meeting minutes. Note that since the use of incorrect IMP will be considered a protocol violation and will not be included in the PP analysis set, for treatment assignment in the PP analysis set, “as randomized” will coincide with “as treated”.

The PP analysis set will serve as the supportive population for the primary efficacy analysis only.

4. GENERAL ISSUES FOR DATA ANALYSIS

4.1. General

Descriptive statistics for continuous variables include n, mean, SD, standard error (SE), median, minimum, and maximum. Descriptive statistics for categorical variables include patient counts and percentages, missing category will be displayed as appropriate.

Inferential statistics for repeated measures and analysis of covariance (ANCOVA) analyses include least squares (LS) mean and SE of the LS mean, estimated treatment difference, 95% confidence interval (CI), and p-value.

For patients who prematurely discontinued study IMP participation for any reason but remain in the study for their scheduled weekly efficacy evaluation, data collected on other alternative therapies received after IMP discontinuation are defined as “retrieved dropout” data.

Data values which are deemed implausible from a clinical perspective (eg, post-randomization pre-bronchodilator percent predicted FEV₁ is $\geq 200\%$ while the baseline FEV₁ was $\leq 85\%$ as required by the protocol Inclusion/Exclusion criteria) will be identified and assessed at the SDR meeting and before unblinding of the database. Any percent predicted FEV₁ values that are $\geq 200\%$ will be treated as missing and excluded from all data analyses. Exclusion of data values will be documented and justified in the clinical study report.

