9.5.4.2. Sensitivity Analysis to Missing Data

To assess the impact of missing data, several sensitivity analyses will be conducted for the 2 endpoints by evaluating alternative estimands. More details will be provided in the statistical analysis plan.

- The primary analysis for the 2 endpoints will be repeated when using data collected after IMP discontinuation (retrieved dropout data). Reference-based imputation will be used only for patients with no retrieved dropout data. This analysis estimates different estimands, namely the change from baseline as actually taken (see estimand 1 in [Mallinckrodt et al 2016](#)).
- The primary analysis for the 2 endpoints will be repeated on completers with no major protocol violations (see estimand 3 in [Mallinckrodt et al 2016](#)).
- A tipping point analysis will be performed as a sensitivity analysis to missing data by utilizing multiple imputations under different missing mechanism. For placebo patients, in all applications of multiple imputations, missing at random (MAR) will be assumed. For the active arms, in the first application, MAR will be assumed and the imputations will be drawn from data in the corresponding active arms. In subsequent applications,

shifts to the distribution of the active arms will be applied to represent different degrees of effect loss, ie, MNAR will be assumed. This analysis will utilize only data collected prior to IMP discontinuation. Additional details will be provided in the SAP.

- “2-dimensional tipping point” multiple imputation will be performed similar to above, the shifts to the distribution will apply to both placebo and active arms, to represent different degrees of effect loss. This analysis will utilize only data collected prior to IMP discontinuation. Additional details will be provided in the SAP.
- The primary analysis for the 2 endpoints will be repeated when missing data will be imputed using a mixed approach of last observation carried forward (LOCF) and baseline observation carried forward (BOCF) as follows: BOCF will be used for patients who had a positive change from baseline at the time of study or IMP discontinuation (ie, a change of 0), while LOCF will be used for patients that have negative change from baseline. In this imputation method, the imputed value is the lower between LOCF and BOCF for each patient. No adjustments will be made to other patients.

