9.5.4.3. Secondary Efficacy Analysis

For all secondary endpoints, analyses will be performed using the ITT analysis set and will not include retrieved dropout data in the analysis.

Analysis of change from baseline in weekly average of daily trough morning PEF, total daily use of albuterol/salbutamol, total daily asthma symptom score, and C-ACT score over the 12-week treatment period will be analyzed using an MMRM analysis with effects due to baseline, sex, age, (pooled) investigational center, previous therapy (ICS or NCS), treatment, time, and time-by-treatment interaction. For all of these endpoints, the MMRM will use only observations collected until IMP discontinuation.

The time to first onset of effect, defined as the first decrease from baseline in daily rescue medication use, will be analyzed using a log-rank test. Median and mean time to first onset of effect and associated 95% CIs will be estimated. Time to first onset of effect will also be displayed graphically with a Kaplan-Meier figure.

The proportion of patients who discontinued from IMP for asthma exacerbation during the 12-week treatment period will be analyzed using a logistic regression model with effects due to previous therapy (ICS or NCS) and treatment. These patients will be considered as nonresponders in this analysis.

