9.5.4.4. Other Efficacy Analysis

Statistical methods to be used for other efficacy endpoints will be described and detailed in the statistical analysis plan.

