6.3.2. Analysis Methods for Secondary Efficacy Variables

The analysis of the secondary efficacy variables will be performed on the ITT analysis set without retrieved dropout data.

6.3.2.1. Change from Baseline in the Weekly Average of Daily Trough Morning (Predose and Prerescue Bronchodilator) Peak Expiratory Flow (PEF) Over the 12-week Treatment Period

The analysis of change from baseline in the weekly average of daily morning (predose and pre-rescue bronchodilator) PEF over the 12-week treatment period will be performed using an MMRM with effects due to baseline weekly average of daily morning PEF, sex, age, (pooled) investigational center, previous therapy (ICS or NCS), week, treatment, and week-by-treatment interaction. No explicit structure will be assumed for the covariance among the repeated measures. However, if there is a convergence problem with unstructured covariance, then a compound symmetry covariance structure will be assumed.

6.3.2.2. Change from Baseline in the Weekly Average of Total Daily (24-hour) use of Albuterol/Salbutamol Inhalation Aerosol (Number of Inhalations) Over Weeks 1 Through 12

The change from baseline in the weekly average of total daily (24-hour) use of albuterol/salbutamol inhalation aerosol (number of inhalations) over weeks 1 through 12 will be analyzed using an MMRM with effects due to baseline value, sex, age, (pooled) investigational center, previous therapy (ICS or NCS), week, treatment, and week-by-treatment interaction. No explicit structure will be assumed for the covariance among the repeated measures. However, if there is a convergence problem with unstructured covariance, then a compound symmetry covariance structure will be assumed.

6.3.2.3. **Change from Baseline in the Weekly Average of the Total Daily Asthma Symptom Score (Defined as the Average of the Daytime and Nighttime Scores) Over Weeks 1 Through 12**

The change from baseline in the weekly average of the total daily asthma symptom scores over weeks 1 through 12 will be analyzed using an MMRM with effects due to baseline score, sex, age, (pooled) investigational center, previous therapy (ICS or NCS), week, treatment, and week-by-treatment interaction. No explicit structure will be assumed for the covariance among the repeated measures. However, if there is a convergence problem with unstructured covariance, then a compound symmetry covariance structure will be assumed.

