6.4.2. Analysis Methods for Other Efficacy Variables

The analysis of the other efficacy variables will be performed on the ITT analysis set without retrieved dropout data.

6.4.2.1. Change from Baseline in the Weekly Average of the Total Daily (24-hour) use of Albuterol/Salbutamol Inhalation Aerosol (Number of Inhalations) at Weeks 4, 8, and 12

The change from baseline in weekly average of total daily (24-hour) use of albuterol/salbutamol inhalation aerosol (number of inhalations) at weeks 4, 8, and 12 will be analyzed using an MMRM with effects due to baseline value, sex, age, (pooled) investigational center, previous therapy (ICS or NCS), week, treatment, and week-by-treatment interaction. No explicit structure will be assumed for the covariance among the repeated measures. However, if there is a convergence problem with unstructured covariance, then a compound symmetry covariance structure will be assumed.

6.4.2.2. Change from Baseline in the Percentage of Rescue-free Days (Defined as 24-hour Periods with no Rescue Medication Usage) During the 12-week Treatment Period

The change from baseline in the percentage of rescue-free days (defined as 24-hour periods with no use of rescue medication recorded in the morning and evening) as recorded in the patient diaries during the 12-week treatment period will be summarized and compared between treatment groups using the Wilcoxon-Mann-Whitney test.

Example SAS code for this analysis:

```
proc npar1way data=salf wilcoxon;
  where treat in ("A", "D");
  class treat;
  var change;
  output out=yyy wilcoxon; run;
```

where: change is the change from baseline in percentage of rescue-free days. The code is executed for each pair of treatment comparisons of interest.

6.4.2.3. Change from Baseline in the Percentage of Symptom-free Days (Defined as 24-hour Periods with Asthma Symptom Score of 0) During the 12-week Treatment Period

The change from baseline in the percentage of symptom-free days (defined as 24-hour periods with asthma symptom scores of zero) as recorded in the patient diaries during the 12-week treatment period will be summarized and will be compared between treatment groups using the Wilcoxon-Mann-Whitney test.

6.4.2.4. Change from Baseline in the Percentage of Asthma-control Days (Defined as 24-hour Periods with Asthma Symptom Score of 0 and no Rescue Medication usage) During the 12-week Treatment Period

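### SAP Section 4.1 defines retrieved dropout data more narrowly than the protocol, so off-drug readings taken without a switch of therapy have no stated SAP exclusion

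*SAP*

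**What the plan says.** SAP Section 4.1 starts with a broad group: "For patients who prematurely discontinued study IMP participation for any reason but remain in the study". For that group it then labels only part of the data: "data collected on other alternative therapies received after IMP discontinuation are defined as" retrieved dropout data.

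Protocol Section 9.5.4.2 sets no condition on therapy. It describes a repeat of the primary analysis "when using data collected after IMP discontinuation (retrieved dropout data"). For the secondary endpoints analysed by MMRM, Protocol Section 9.5.4.3 adds an explicit rule: "the MMRM will use only observations collected until IMP discontinuation".

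The SAP does not restate that rule. Section 6.3.2 says: "The analysis of the secondary efficacy variables will be performed on the ITT analysis set without retrieved dropout data". Section 6.4.2 says: "The analysis of the other efficacy variables will be performed on the ITT analysis set without retrieved dropout data". The subgroup summaries in Section 6.2.3 and the MMRM sensitivity analysis in Appendix E exclude data through the same label and nothing else.

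For the other efficacy endpoints, Protocol Section 9.5.4.4 sets no rule of its own: "Statistical methods to be used for other efficacy endpoints will be described and detailed in the statistical analysis plan".

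The SAP's introduction says that the SAP is meant to agree with the protocol, and that it takes precedence where the two differ. Section 11 reports no change to the protocol's analyses apart from a clarification of the per-protocol set.

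**The concern.** Protocol Section 3.4 allows IMP to be withdrawn for reasons such as an adverse event, noncompliance or a protocol violation, while the child stays in the study and completes the remaining visits. Such a child may take no alternative asthma therapy, or may start it only later. The readings in between are off drug. They are retrieved dropout data under the protocol but not under a literal reading of SAP 4.1.

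If a programmer builds the exclusion flag from SAP 4.1, those readings enter the affected analyses alongside on-treatment values. In an active arm they would be expected to pull the estimate toward placebo. Those analyses would also follow a different on-treatment rule from the primary analysis, and the reader of the report would not be told.

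**Working it through.** The plan states no figure on this point, so the check is mainly a comparison of the rules for each analysis.

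| Analysis | How the SAP removes post-IMP data | Protocol rule behind it | Exposed? |
|---|---|---|---|
| Primary (SAP 6.2.2, Appendix A) | Every premature IMP stopper is imputed from placebo data, whatever was retrieved | Same approach, 9.5.4.1 | No |
| Both tipping-point analyses (SAP 6.2.2.3) | Own cut at IMP discontinuation | Same cut, 9.5.4.2 | No |
| Four secondary MMRMs (SAP 6.3.2.1 to 6.3.2.4) | Label only | Explicit cut, 9.5.4.3 | The documents are at odds |
| Time to first onset (SAP 6.3.2.5) | Label; non-events censored at the IMP discontinuation visit | Label in the broad sense, 9.5.4.3 | Little |
| Proportion discontinued for exacerbation (SAP 6.3.2.6) | Discontinuation is itself the event | Not needed | No |
| Other endpoints (SAP 6.4.2) | Label only; time to consistent onset also censors non-events at that visit | None; 9.5.4.4 defers to the SAP | Yes |
| Subgroup summaries (SAP 6.2.3) | Label only | Subgroups named in 9.5.4, no cut given | Yes, descriptive only |
| MMRM sensitivity analysis (SAP Appendix E) | Label only, though likened to the primary estimand | Label in the broad sense, 9.5.4.2 | Ambiguous |

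**An example.** Suppose a child stops IMP at the week 4 visit because of an adverse event, stays in the study and starts no other asthma therapy. The primary trough analysis imputes the week 12 value. Under SAP 6.4.2 with the 4.1 definition, nothing excludes the evening PEF averages for weeks 5 to 12 (12 − 4 = 8 weekly values) or rescue use at weeks 8 and 12. The completeness rule for rescue-free, symptom-free and asthma-control days (SAP 6.4.1.1 to 6.4.1.3) would not remove such days either. It counts against the 12-week period or the child's days in the study, not days on IMP.

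**Scale.** The documents do not say how many children stop IMP, stay in the study and do not switch. The nearest figures are in SAP Section 6.2, from a 6-week study in patients aged 12 and over:

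- IMP discontinuation: 11.2% on placebo, 3.1% on pooled active.
- Withdrawal for worsening asthma: 9.3% on placebo, 0.6% on pooled active.
- Stopped for another reason: 11.2 − 9.3 = 1.9% on placebo; 3.1 − 0.6 = 2.5% on active.
- Per arm of 206: 206 × 0.019 ≈ 4 on placebo; 206 × 0.025 ≈ 5 on active.
- As a share of all stoppers: 1.9/11.2 ≈ 17% on placebo; 2.5/3.1 ≈ 81% on active.

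The unknown is what fraction of these other stoppers stay in the study untreated. Letting that fraction run from none to all gives 0 to about 4 children on placebo and 0 to about 5 in each active arm. If all do, the label would miss most active stoppers but few placebo stoppers, so the exclusion would act unevenly by arm. The range omits any off-drug days before a later switch, and rates over 12 weeks in children may differ.

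**The case against.** The strongest reply is that Section 4.1 is one awkward sentence and that the SAP otherwise uses the term broadly. The sentence itself covers stopping for any reason. In Section 6.2.2.3 the analysis with retrieved dropout data takes in whatever efficacy data could be collected after discontinuation, with no therapy condition. The tipping-point analysis is introduced there as being without retrieved dropout data and is then cut at IMP discontinuation, which treats the two phrases as equivalent. This is good evidence that the intent was broad. It does not remove the conflict, because 4.1 is where the SAP defines the term and is the natural source for a derivation flag.

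A reader might infer more: that the SAP has decided to keep off-drug readings as on-treatment values in all secondary, other and MMRM analyses. The documents do not support that. For the four secondary MMRMs the protocol's cut still stands, the SAP is silent rather than contradictory, and Section 11 reports no change. Retention follows only if that silence plus the narrow label counts as a difference in which the SAP prevails.

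A reader might also try to put a power loss on the gap. The planning inputs (SD 22% with 6.5%, SD 17% with 5%) belong to the two primary FEV₁ tests, which are protected. No SD or expected difference is given for PEF, rescue use, symptom score or C-ACT. The 12% planning dropout rate is not the rate of stopping IMP and staying in the study untreated. Finally, asthma therapy is to be discussed and recorded at the IMP discontinuation visit, which makes long untreated follow-up less likely, though not impossible.

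**Conclusion.** The point holds as a conflict of definitions. SAP 4.1 is narrower than Protocol 9.5.4.2 and than the SAP's own use in 6.2.2.3, and Section 11 does not declare the change. Readings taken after IMP is stopped, without a switch or before one, therefore have no stated SAP exclusion wherever the label is the only filter. The gap is clearest for the other efficacy endpoints, which have no protocol cut to fall back on. For the four secondary MMRMs, the two documents need to be brought into line.

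The effect is probably small: 0 to about 5 children per arm on the illustration above, which assumes that the cited older population is a fair guide and that only stoppers without worsening asthma go untreated. The likely direction in the active arms is toward placebo. No primary conclusion, significance level or sample size depends on it.

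**What to change.** In SAP 4.1, define retrieved dropout data as all efficacy data collected after IMP discontinuation, whether or not alternative asthma therapy has started. In SAP 6.3.2, 6.4.2, 6.2.3 and Appendix E, state that only data up to IMP discontinuation are used, in line with Protocol 9.5.4.3. If the narrow definition was in fact intended, Section 11 should say so and give the reason.

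The cost is one definition, a short statement of the cut in four places and one derivation flag, all before database lock. No new data are needed.

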4.2. Specification of Baseline Values

In general, the baseline values for efficacy and safety variables are defined as the last observed data before the first dose of study drug, unless otherwise noted.

For data collected daily in electronic patient diaries (ie, daily FEV₁, PEF, asthma symptom scores, rescue medication use, etc.), baseline is defined as the average of daily data recorded in the 7 days before randomization. The prerandomization day consists of the electronic patient diary entries on the evening prior to the RV (TV1) or on the morning of the RV (TV1) for evening or morning FEV₁ and PEF values, respectively. The first postbaseline record is the data collected after the first dose on the evening of the RV (TV1). Patients have to record baseline values on at least 5 out of the last 7 days prior to the RV in order to be randomized, nonetheless, a few patients who were randomized with less than 5 nonmissing values. To eliminate number of missing baseline values, rules for handling missing electronic patient’s diaries are specified below.

Weekly Average Percent Predicted Trough Morning FEV₁ and Trough Morning PEF:

The baseline percent predicted trough morning FEV₁ or trough morning PEF is defined as the average of recorded (nonmissing) percent predicted trough morning FEV₁ or trough morning PEF assessments over the 7 days prior to randomization. The first day before randomization consists of the electronic patient diary entry at **home** on the morning of the RV (TV1). A patient has to record trough morning FEV₁ and trough morning PEF values on at least 5 out of the last 7 days prior to the RV in order to be randomized. In case there are less than 5 non-missing values, the trough morning FEV₁ or trough morning PEF record will include days beyond 7 days prior to the randomization to ensure that the baseline value can be calculated. If a minimum of

5 nonmissing values cannot be satisfied during the entire run-in period (14-30 days), the patient's percent predicted trough morning FEV₁ or trough morning PEF baseline values will be replaced by the overall baseline value.

1-Hour Percent Predicted Trough Morning FEV₁:

The baseline 1-hour percent predicted trough morning FEV₁ is defined as the predose percent predicted trough morning FEV₁ measurement at the RV (TV1) at the **investigational center**. If the predose FEV₁ measurement is missing or the value is implausible, the baseline weekly at home average percent predicted trough morning FEV₁ will be used. If both, the baseline pre-dose FEV₁ measurement and the baseline weekly average percent predicted trough morning FEV₁ are missing, the baseline trough morning FEV₁ will be replaced by the overall baseline 1-hour value.

Trough Evening PEF:

The baseline trough evening PEF is defined as the average of recorded (nonmissing) trough evening PEF assessments over the 7 days prior to randomization. The first day before randomization consists of the electronic patient diary entry on the evening before the RV (TV1). Five out of the last 7 days nonmissing values are required for a patient to be randomized and to calculate the baseline value. In case the minimum of 5 nonmissing values cannot be satisfied during the entire run-in period (14-30 days), the patient's evening PEF baseline value will include days beyond 7 days prior to the randomization. If a minimum of 5 nonmissing values cannot meet, missing baseline value will be replaced by the overall trough evening PEF value.

Total Daily (24-Hour) Use of Albuterol/Salbutamol Inhalation Aerosol (Number of Inhalations):

Throughout the study albuterol/salbutamol inhalation aerosol will be provided to patients to be used as needed for the relief of asthma symptoms. Patients will record intake (number of inhalations) of rescue medication each morning and evening in the electronic patient diary. An entry of zero inhalations for both morning and evening will indicate a rescue-free 24-hour period.

The baseline value is defined as the average number of inhalations over each 24-hour (day and night) period over the 7 days prior to the date of the first dose. Patients should withhold their rescue medication for at least 6 hours prior to the morning of the RV (TV1), and all other study visits. Five out of last 7 days nonmissing values are required for patient to be randomized. No missing data imputation rule will apply.

Percentage of Rescue-free Days (24-Hour Periods):

A rescue-free day is defined as a 24-hour period with no use of rescue medication recorded. The baseline percentage of rescue-free days is defined as the percentage of rescue-free days over the 7 days prior to the RV. An entry of zero inhalations for both morning and evening will indicate a rescue-free 24-hour period.

Total Daily (24-Hour) Asthma Symptom Score:

The total daily asthma symptom score is defined as the average of the daytime and nighttime scores. The baseline total daily asthma symptom score is defined as the average of recorded (nonmissing) total daily asthma symptom scores over the 7 days prior to randomization. Five out of the last 7 nonmissing values are required for a patient to be randomized. If a minimum of

5 nonmissing values cannot be satisfied during the entire run-in period (14-30 days), the patient's asthma symptom score will include days beyond 7 days prior to the randomization or replaced by the overall asthma symptom score. No missing data imputation rule will apply.

Percentage of Symptom-free Days (24-Hour Periods):

Symptom-free days are defined as 24-hour periods with asthma symptom scores of zero recorded on the asthma symptom score electronic patient diary for both morning and evening entries. The baseline is defined as the percentage of symptom-free days over the 7 days prior to randomization.

A 24-hour symptom-free period is associated with a score of zero on the asthma symptom score diary for both morning and evening entries. Should either the morning or evening entry be missing and the other value is equal to zero, the available value will be weighted by half, and similarly the denominator will be modified to reflect the missing value. If both, morning and evening values, are missing for a particular day, the value will not be used in the calculation of percentage. [Table 2](#) illustrates a week of baseline symptom score and imputation rules as recorded in the electronic patient diary.

Table 2: An Example of Baseline Electronic Patient Diary Data for Symptom-free Days

Analysis Day	Morning score	Evening score	Value used for numerator of percentage calculation	Value used for denominator of percentage calculation
1	3	0	0	1
2	Missing	Missing	Not used in calculations	Not used in calculations
3	0	0	1	1
4	1	3	0	1
5	Missing	2	0	1/2
6	Missing	0	1/2	1/2
7	0	0	1	1
Week's total			2.5	5

The percent of symptom-free 24-hour periods for this example is derived as $2.5/5 * 100\% = 50\%$. Similar rules apply to on-therapy interval.

Percentage of Asthma-control Days (24-Hour Periods):

Asthma-control days are defined as scores of zero recorded on the asthma symptom score diary during the 24-hour period and no rescue medication usage during the same 24-hour period. The baseline is defined as the percentage of asthma-control days over the 7 days prior to randomization. Detailed imputation rules are specified in [Table 3](#).

Table 3: An Example of Baseline Electronic Patient Diary for Asthma-control days

Analysis Day	Total Daily Asthma Score / Rescue Medication Usage	Value used for numerator of percentage calculation	Value used for denominator of percentage calculation
-1	3 / 0	0	1
-2	Missing / 0	Not used in calculations	Not used in calculations
-3	0 / 0	1	1
-4	Missing / 3	0	1
-5	0 / 3	0	1
-6	3 / 3	0	1
-7	Missing / Missing	Not used in calculations	Not used in calculations
Week's total		1	5

The percent of asthma-control days for this example is derived as $1/5 * 100\% = 20\%$. Note that if a patient's asthma score is missing, and there is no rescue medication usage during the same 24-hour period, the asthma-control days will not be used in calculations.

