6.4.1.2. Percentage of Symptom-free 24-Hour Periods

The asthma symptom scores are specified in Section 6.3.1.3. Scores of zero for both morning and evening indicate a 24-hour symptom-free period. The calculations of the percentage of symptom-free 24-hour periods will be based on the weekly analysis day data recorded during the treatment period. The missing data will be imputed according to the rules specified in Table 2. A minimum of 60% of full days during the 12-week treatment period (or relative to the number of days that the patient participated in the study) cannot be missing in order for a patient to be included in this analysis.

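### SAP Table 2 gives a half denominator to a half-recorded day already known to be symptomatic, which the Section 4.2 text does not provide for and which overstates the percentage of symptom-free days

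*SAP*

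**What the plan says.** SAP Section 4.2, under the percentage of symptom-free days, makes three statements.

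- Definition: "A 24-hour symptom-free period is associated with a score of zero on the asthma symptom score diary for both morning and evening entries".
- One entry missing: should either entry "be missing and the other value is equal to zero, the available value will be weighted by half". The rest of that conditional sentence turns to the denominator: "and similarly the denominator will be modified to reflect the missing value".
- Both entries missing: "If both, morning and evening values, are missing for a particular day, the value will not be used in the calculation of percentage".

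Table 2 is offered as an illustration of a baseline week under these rules. Its columns are day, morning score, evening score, numerator and denominator. Day 5 reads "5 Missing 2 0 1/2" and day 6 reads "6 Missing 0 1/2 1/2". Day 1, with morning 3 and evening 0, has numerator 0 and denominator 1.

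Below the table: "The percent of symptom-free 24-hour periods for this example is derived as" 2.5/5, or 50%. The next sentence extends similar rules to the on-therapy interval. Section 6.4.1.2 does the same for the treatment-period percentage: "The missing data will be imputed according to the rules specified in" Table 2.

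The endpoint is the change from baseline in this percentage. It is compared between arms by a Wilcoxon-Mann-Whitney test (Section 6.4.2.3), with no multiplicity adjustment for this class of endpoint (Section 7.2).

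**The concern.** A half weight makes sense when half of the day is unrecorded and the day's status is therefore open. Day 6 is such a day: the evening was clear and the morning is unknown. Day 5 is not. A recorded score of 2 settles the matter, and no morning entry could make the day symptom-free. Days 1 and 5 both fail on a single nonzero entry. One counts fully and the other counts half, only because a diary entry was skipped.

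The half-weight sentence is conditional on the recorded entry being zero, and no sentence covers a missing entry beside a nonzero one. A programmer who works from the definition and that condition would code day 5 as 0 out of 1. One who copies the table would code it as 0 out of 1/2. The two derived datasets would differ. Under the table's version, leaving half the diary blank on a bad day raises the patient's percentage.

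**Working it through.** **Inputs.** All scores, numerators and denominators are from SAP Table 2. The definition and the half-weight condition are from the text of Section 4.2.

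**1. Reproduce the plan's figure.** Day 2 is dropped because both entries are missing.

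- Numerator, days 1, 3, 4, 5, 6, 7: 0 + 1 + 0 + 0 + 1/2 + 1 = 2.5.
- Denominator, same days: 1 + 1 + 1 + 1/2 + 1/2 + 1 = 5.
- 2.5/5 = 50%. The addition and division are correct.

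**2. Count day 5 as a full failed day.** The numerator is unchanged at 2.5. The denominator is 1 + 1 + 1 + 1 + 1/2 + 1 = 5.5, and 2.5/5.5 = 45.5%. The difference is 4.5 percentage points.

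**3. Check against the definition.** Six days have at least one entry. Days 3 and 7 are symptom-free; days 1, 4 and 5 are not; day 6 is open. The true share of these six days is 2/6 = 33.3% if day 6 fails and 3/6 = 50% if it does not. The printed 50% is the upper limit.

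**4. A week in which nothing is open (assumed pattern).** Take 3 symptom-free days, 2 fully recorded symptomatic days and 2 half-recorded symptomatic days. Every day's status is known.

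- Definition: 3/7 = 42.9%.
- Table 2 rule: 3/(3 + 2 + 2 × 1/2) = 3/6 = 50%.

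The excess of 7.1 points comes from the weighting alone.

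**5. Range for other seven-day weeks (assumed patterns).** With s symptom-free days and k half-recorded symptomatic days, the Table 2 rule gives s/(7 − k/2) and full weight gives s/7.

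| s | k | Table 2 rule | Full weight | Excess (points) |
|---|---|---|---|---|
| 2 | 1 | 30.8% | 28.6% | 2.2 |
| 3 | 2 | 50.0% | 42.9% | 7.1 |
| 4 | 3 | 72.7% | 57.1% | 15.6 |

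With s = 0 both rules give 0%, so a patient with no symptom-free credit is unaffected.

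**6. All half-recorded days together, including those like day 6.** Let q be the chance that the recorded half is zero, and r the chance that the missing half is also zero given that the recorded half is. Take missingness as unrelated to the scores. On these days:

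- true symptom-free share: q × r
- Table 2 rule: (q/2)/(q/2 + (1 − q)/2) = q
- day 5 at full weight: (q/2)/(q/2 + (1 − q)) = q/(2 − q)

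| q | True, halves independent (r = q) | True, halves always agree (r = 1) | Table 2 rule | Full weight |
|---|---|---|---|---|
| 0.6 | 36% | 60% | 60% | 43% |
| 0.8 | 64% | 80% | 80% | 67% |

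Full weight overstates when r is below 1/(2 − q), which is 0.71 at q = 0.6 and 0.83 at q = 0.8, and understates when r is above it. Neither q nor r is in the documents; 0.6 to 0.8 is an assumed range.

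**The case against.** **The table fills a gap in the text.** The text gives no denominator for a missing entry beside a nonzero one, and Section 6.4.1.2 names Table 2 as the source of the rules. On that view the table cell is the only explicit instruction and nothing contradicts it. The table also has its own logic: each recorded half-day adds 1/2 to the denominator. It stands that the text is silent on this case, so this is not two explicit rules in conflict. But the half weight is tied to a zero score, the table is presented as an illustration of that text, and step 4 shows the cell departing from the definition when every day's status is known.

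**Full weight has an asymmetry of its own.** It gives half-recorded bad days full weight and half-recorded clear days half weight. If the two halves of a day usually agree, Table 2 is close to right on half-recorded days as a group, and full weight reads low. This stands as a limit on any claim about overall bias. It does not justify the day 5 cell, because what is uncertain is the day 6 type of day.

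**The consequence may be small.** The same rule applies before and after randomization and in every arm. Randomization requires day and night scores on at least 5 of 7 days (protocol Section 5.9), although SAP Section 4.2 notes that a few patients fell short. Inclusion in this analysis requires at least 60% full days (Section 6.4.1.2). Partial cancellation in the change score is plausible. It is not assured, since these limits allow up to 2/7 = 29% incomplete days at baseline and 40% on treatment.

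**Table 3 might be read as settling the matter.** Its day -4, shown as missing / 3, counts 0 out of 1, and a reader might infer that the SAP treats the same situation in two ways. It does not. The 3 there is rescue use, the missing item is the total daily score, and the endpoint is asthma-control days. That table drops its missing / 0 day instead of half-weighting it. Under Section 6.3.1.3 the total score is missing if either half is missing, so a day like day 5 with no rescue use would be left out of Table 3 altogether. Table 3 supports only the general principle that a day known to fail counts fully.

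**Conclusion.** The point holds as an inconsistency between the Section 4.2 definition and half-weight condition on one side and the day 5 cell of Table 2 on the other. Compared with full weight, the half denominator can only raise a patient's percentage or leave it at zero. The printed example is 4.5 points above the value with day 5 at full weight. In the assumed weeks shown, the excess runs from 2.2 to 15.6 points.

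Three stronger conclusions might be inferred, and the documents support none of them.

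- That Table 2 is mis-added. It is not; the fault is in a weight.
- That symptom-free days in the trial are overstated by a known amount. Setting 36% to 64% against 60% to 80% requires independent morning and evening symptoms, which nothing in the documents supports. Whether the fix over- or under-corrects on half-recorded days overall depends on within-day agreement and diary missingness, and neither is given.
- That a treatment comparison is biased. None is shown to be.

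Primary and secondary endpoints are not touched. This is a minor correction, worth making because the derivation is otherwise ambiguous.

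**What to change.** In SAP Table 2, set the day 5 denominator to 1 and the column total to 5.5, and give the example below the table as 2.5/5.5 = 45.5%. Add one sentence to Section 4.2: any recorded nonzero symptom score makes the day 0 out of 1, whether or not the other entry is present. Section 6.4.1.2 then inherits the corrected rule for the treatment period through its reference to Table 2.

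If the sponsor does intend a half denominator for such days, the text should say so and give the reason. Either way, text and table should agree before database lock. The cost is one cell, its total, one percentage and one sentence.
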